6.6. General Medical History

Medical history of subjects prior to dosing captured in Study 401GSDIA01 is summarized and listed as part of the clinical study report for that study. Medical history prior to study entry will also be collected at Visit 1 in Study 401GSDIA02 and will mainly include any AEs that are ongoing at the completion of Study 401GSDIA01. This data will be listed by subject.

6.7. Prior and Concomitant Medication

Prior medications are defined as medications that started before the dosing and they are summarized and listed as part of Study 401GSDIA01 Clinical Study Report. Concomitant medications are defined as any medications taken on or after the dosing date. Concomitant medications from Study 401GSDIA01 are summarized and listed as part of its clinical study report. Concomitant medications data captured in Study 401GSDIA02 will be summarized separately. Further, concomitant medications data from both studies 401GSDIA01 and 401GSDIA02 will be combined and summarized and listed as well. Concomitant medications will be coded by drug name and therapeutic class using WHO Drug dictionary. If a subject received a specific medication multiple times or received multiple medications within a specific therapeutic class, that subject will be counted only once for the coded drug name or therapeutic class.

6.8. Efficacy Analysis

The efficacy analyses will be based on the Full Analysis Set.

6.8.1. Symptom-Free Euglycemia (Controlled Fasting Challenge)

Subject's ability to maintain symptom-free euglycemia during controlled fasting challenge (CFC) will be measured by the time to first hypoglycemic event during CFC or equivalently the duration of CFC. Duration of CFC is defined as time (in hours) from start of CFC to the end of CFC (as documented on eCRF). CFC ends when any of the following 3 conditions are met: 1) glucose <54 mg/dL; 2) signs/symptoms of hypoglycemia; or 3) 15 hours fasting without hypoglycemia. Change from baseline will be calculated using results on Day 0 in Study 401GSDIA01 as baseline.

Data from both studies 401GSDIA01 and 401GSDIA02 will be included in this analysis. Duration of CFC and change from baseline will be summarized by visit. Use of cornstarch and carbohydrates in the dinner prior to controlled fasting challenge and change from baseline will be summarized by visit. A listing of CFC data will be provided.

Since subjects can receive different amounts of carbohydrates in their dinner and cornstarch prior to the CFC due to individualized prescription for their meals and cornstarch, a summary of duration of CFC normalized by amount of cornstarch consumed before the CFC and change from baseline will be provided. Normalized CFC duration will be calculated as CFC duration divided by the pre-CFC cornstarch (grams) and it will denote the gain in CFC duration (in minutes) per gram of cornstarch. Similarly, a summary of duration of CFC normalized by amount of carbohydrates consumed before the CFC and change from baseline will be provided. Normalized CFC duration will be calculated as CFC duration divided by the sum of carbohydrates in the dinner and cornstarch prior to the CFC and it will denote the gain in CFC duration (in minutes) per gram of carbohydrates.

Plots for individual patient profile of CFC duration and change from baseline in CFC duration by visit will be provided. Additional plots will include CFC duration (and change from baseline) and indicators for inappropriately high insulin level or inappropriately low cortisol levels during the CFC if that data is collected during the CFC. Insulin response is deemed inappropriate if ≥ 25 $\mu\text{IU/mL}$ at the start of the challenge or $> 2\mu\text{IU/L}$ at the end of the challenge. Cortisol response is deemed inappropriate if < 10 $\mu\text{g/dL}$ at the end of the challenge. Plots will also be provided for normalized CFC duration (by the amount of pre-CFC cornstarch).

Pre-CFC whole blood lactate and rate of rise of lactate during the CFC (calculated as the slope between the lactate value at the start of CFC and peak lactate value during the CFC, expressed as mmol/L/h) and change from baseline will be summarized by visit. Pre-CFC analyte value is the value collected nearest to the start time of the CFC and within ± 30 minutes of start time of CFC. End-CFC analyte value is the value collected nearest to the end time of the CFC and within ± 30 minutes of end time of CFC. Peak analyte value during the CFC is the maximum analyte value observed any time from the start time of CFC to the end time of the CFC and including pre-CFC and end-CFC analyte values.

Similarly, pre-CFC plasma glucose and rate of decline of glucose during the CFC and change from baseline will be summarized by visit. Trough analyte value during the CFC is the minimum analyte value observed any time from the start time of CFC to the end time of the CFC, including pre-CFC and end-CFC values (defined above). Rate of decline of glucose will be calculated as the slope between the pre-CFC glucose value and trough glucose value during the CFC, expressed as mg/dL/h .

In addition, plots for individual patient profile of glucose and lactate levels during CFC will be presented by study visits. Plot for individual patient profile of glucose and ketones levels during CFC will be presented by study visit where that data was collected.

A listing of metabolic lab parameters (glucose, lactate, ketones, free fatty acids, alanine), and hormonal lab parameters (cortisol, ACTH, glucagon, insulin, C-peptide, growth hormone, IGFBP1) collected before and during the controlled fasting challenges will be provided.

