12.5. Efficacy Analyses

12.5.1. Symptom-Free Euglycemia

Symptom-free euglycemia will be measured using the duration of controlled fasting challenge. Duration of controlled fasting challenge is defined as time to any of the following 3 conditions: 1) glucose <54 mg/dL (<3.0 mmol/L); 2) signs/symptoms of hypoglycemia; or 3) 15 hours fasting without hypoglycemia. Change from Baseline will be provided where Day 0 in Study 401GSDIA01 is considered as baseline.

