2.2. Secondary Objective(s) and Endpoint(s)

The secondary objective of the study is as follows:

- To evaluate the long-term effect of DTX401 on symptom-free euglycemia in a setting of a controlled fasting challenge

The secondary endpoint of this study is as follows:

- The change from Day 0 (Study 401GSDIA01) in time to first hypoglycemic event during a controlled fasting challenge over time by cohort and overall, following IV administration of DTX401

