6. STATISTICAL ANALYSIS

6.1. General Principles

All analyses in the study will be descriptive; no formal hypotheses will be tested. An integrated analysis using data from both Study 401GSDIA01 and Study 401GSDIA02 will be performed to summarize and assess the long-term safety and efficacy of DTX401; there will not be a standalone analysis of data from only Study 401GSDIA02.

Continuous variables will be summarized by number of subjects, mean, SD, standard error (SE), median, Q1, Q3, minimum, and maximum values. Categorical variables will be summarized by number and percentage of subjects. All summary tables will be presented by scheduled study visit and no analysis windows will be used, unless specified otherwise. Study visits from both studies 401GSDIA01 and 401GSDIA02 will be included in summary tables.

All summary tables will be presented by dose cohort of DTX401 (see below), Cohorts 2, 3, 4 combined (i.e., cohorts for dose 2 combined), and overall, unless specified otherwise.

The dosing cohorts are:

- Cohort 1: Dose 1 (2.0×10^{12} GC/kg) with a reactive steroid regimen (prednisone starting dose of 40 mg/day)
- Cohort 2: Dose 2 (6.0×10^{12} GC/kg) with a reactive steroid regimen (prednisone starting dose of 40 mg/day)
- Cohort 3: Dose 2 (6.0×10^{12} GC/kg) with an optimized reactive steroid regimen (prednisone starting dose of 60 mg/day)
- Cohort 4: Dose 2 (6.0×10^{12} GC/kg) with a prophylactic steroid regimen

SAS[®] software version 9.4 or higher will be used to perform statistical analyses unless otherwise specified.

Handling of missing or incomplete data is described in [Appendix 1](#).

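### SAP 6.8.1 wrongly equates time to first hypoglycemic event with CFC duration: fasts that end event-free at 15 h are right-censored, yet they are summarised as ordinary values and never counted

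*SAP*

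**What the plan says.** SAP section 2.2 (and Protocol 12.1.2) defines the secondary endpoint as "The change from Day 0 (Study 401GSDIA01) in time to first hypoglycemic event during a controlled fasting challenge over time by cohort and overall". SAP 6.8.1 then says that the ability to maintain symptom-free euglycemia "will be measured by the time to first hypoglycemic event during CFC or equivalently the duration of CFC". Duration runs from the start to the end of the challenge as recorded on the eCRF. The challenge ends at glucose below 54 mg/dL, at signs or symptoms of hypoglycemia, or at "3) 15 hours fasting without hypoglycemia". Protocol 12.5.1 has the same three endings and states: "Symptom-free euglycemia will be measured using the duration of controlled fasting challenge".

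For the change, SAP 6.8.1 adds: "Change from baseline will be calculated using results on Day 0 in Study 401GSDIA01 as baseline". Duration and change are summarised by visit. The statistics come from SAP 6.1: "Continuous variables will be summarized by number of subjects, mean, SD, standard error (SE"), followed by median, quartiles, minimum and maximum. Tables are by cohort, Cohorts 2 to 4 combined, and overall. SAP 6.8.1 also plans a CFC listing, individual profile plots, and summaries of glucose decline.

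SAP 6.8.1, SAP Appendix 1 and Protocol 12.5.1 contain no censoring rule, no time-to-event method and no count of fasts that reach 15 h event-free. SAP 2.4 marks estimands as not applicable.

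**The concern.** The first two endings are hypoglycemic events. The third, by its own wording, is the absence of one. For that ending, duration is 15 h while time to hypoglycemia is some unknown value above 15 h. A subject who becomes hypoglycemic at 15 h and one who is still euglycemic at 15 h enter the endpoint with the same number.

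The objective is long-term effect, and fasts are scheduled through Week 260 (Protocol 7.1.3.1). Whether effect is kept is therefore the main question for this endpoint, and the limit removes information where response is best. Cohorts have 3 subjects each, so a single capped fast is a third of a cohort's data. The durations normalised by cornstarch or carbohydrate in SAP 6.8.1 inherit the capped numerator.

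This point concerns only the planned ending at 15 h, not fasts stopped early for other reasons.

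**Working it through.** The plan gives no CFC durations, SD or power calculation, so there is no figure of its own to reproduce. The check tests the mechanism under stated assumptions.

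**Inputs.** From the documents: limit 15 h; 12 subjects in 4 cohorts of 3; the summary statistics of SAP 6.1. Assumed: true time to hypoglycemia T is normal with mean m and SD s.

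**Step 1: what the planned mean estimates.** The analysed value is Y = min(T, 15). Take an invented set of 12 true times: 6, 7, 9, 11, 12, 13, 14.5, 15.5, 16, 17, 18, 20 h. Five reach the limit.
- Planned summary: the capped values sum to 147.5, so the mean is 147.5/12 = 12.29 h; SD 3.33, SE 0.96, median 13.8 h.
- Five fasts censored at 15 h: Kaplan-Meier restricted mean to 15 h is 12.29 h, median 13.8 h, event-free proportion at 15 h is 5/12 = 42%.
- True times: mean 13.25 h, SD 4.40, SE 1.27.

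Censoring leaves the mean unchanged when the 15 h limit is the only censoring. What the planned table lacks is the 42% and the correct label.

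**Step 2: how much of a fall is seen.** With z = (15 − m)/s, and φ and Φ the standard normal density and distribution function,

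E[Y] = 15 − s[φ(z) + zΦ(z)].

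For s = 3:
- m = 18: z = −1, E[Y] = 15 − 3(0.2420 − 0.1587) = 14.75 h.
- m = 15: z = 0, E[Y] = 15 − 3(0.3989) = 13.80 h.

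A true fall of 3 h shows as 0.95 h. Varying both the mean and the SD:

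| True mean falls (h) | Seen, SD 2 | Seen, SD 3 | Seen, SD 4 | Share capped at first visit (SD 2 / 3 / 4) |
|---|---|---|---|---|
| 18 to 15 | 0.74 | 0.95 | 1.07 | 93% / 84% / 77% |
| 14 to 11 | 2.62 | 2.36 | 2.19 | 31% / 37% / 40% |
| 10 to 7 | 3.00 | 2.94 | 2.83 | 1% / 5% / 11% |

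The level of the mean drives the result far more than the SD does.

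**Step 3: spread.** Var(Y) = s²[(1 + z²)Φ(z) + zφ(z)] − (15 − E[Y])². With s = 4, the SD of Y is 3.64, 2.67 and 1.33 h at m = 10, 14 and 18 h, which is 0.91, 0.67 and 0.33 of the true SD. The SE for 12 subjects is 1.05, 0.77 and 0.38 h, against 4/√12 = 1.15 h uncapped.

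**Step 4: a single cohort.** If three subjects fall from true times of 18, 20, 22 h to 15.5, 16, 17 h, both visits give mean 15.0 h, SD 0 and SE 0, provided each recorded duration is exactly 15 h.

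**Step 5: direction of the change.** Observed change is min(T, 15) − min(B, 15), with B the true Day 0 time.
- B < 15 and T ≥ 15: observed change is 15 − B, at most the true change (lower bound).
- B ≥ 15 and T < 15: observed change is T − 15, at least the true change (upper bound).
- Both capped: observed change is 0 and the sign is unknown.

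**The case against.** Four stronger readings are tempting, and the documents do not support them.

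- **That the ceiling is hidden.** The 15 h ending is stated in the Protocol synopsis, Protocol 10.4.1 and 12.5.1, and SAP 6.8.1. Minimum, median and maximum, a CFC listing and individual plots are planned. In a 12-subject study a reader could find values at 15 h. What the text does not require is any count or mark showing why a fast ended.
- **That the standard errors are wrong.** For a mean restricted to 15 h they are valid, as Step 1 supports. The plan's fault is that it names a different quantity. No hypothesis test is planned (SAP 3.7), so no error rate is affected. The descriptive tables are, however, the whole evidence, and SAP 3.9 allows administrative analyses in support of registration.
- **That the endpoint masks most of any loss of effect.** This holds only if true times sit near or above the limit, and no durations are given. With true means of about 10 h or less, almost all of a loss is visible. The median is unaffected while fewer than half the fasts are capped. The planned pre-CFC glucose, rate of glucose decline and individual glucose curves also help to separate a comfortable 15 h finish from one just above 54 mg/dL.
- **That a plateau at 15 h would be taken as proof of durability.** Nothing in the documents says so.

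Two further caveats stand. Recorded durations come from eCRF start and stop times, so an SD of exactly 0 is a limiting case. The table shells are kept in a separate document (SAP section 8) and may contain a count, but the SAP text does not require one.

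**Conclusion.** The statement of equivalence is wrong for every fast that ends event-free at 15 h, and this follows from the SAP's own list of endings without any assumption. The planned mean and SE should be read as describing a mean restricted to 15 h; as time to hypoglycemia, they give a lower bound with understated spread.

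The practical size is conditional. Under the assumed normal times, compression of a late decline ranges from severe (roughly two thirds to three quarters of a 3 h fall unseen from 18 to 15 h) to negligible (at most about 6% from 10 to 7 h). Cohort differences are compressed in the same way. The unknown that decides between these is the number of capped fasts, which is the figure the plan does not tabulate. A correction is worth making, but this is a defect of definition and reporting rather than a miscalculation.

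**What to change.** In SAP 6.8.1:

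1. Delete *or equivalently*. State that a fast reaching 15 h without hypoglycemia is censored at 15 h, and label the mean as restricted to 15 h.
2. Add by visit the number and percentage of subjects reaching 15 h event-free, for each cohort, Cohorts 2 to 4 combined, and overall.
3. Show a median or quartile that falls at the limit as ≥15 h.
4. Mark capped fasts on the individual plots.
5. Footnote mean change as a lower bound only where follow-up fasts are capped and the corresponding Day 0 fasts were not.

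The cost is SAP wording, one table row and a plotting symbol. Start and stop times, glucose values and the ending conditions are already part of the challenge record, and no study procedure changes. The table becomes slightly busier. Kaplan-Meier curves for cohorts of 3 are not needed. The change cannot recover differences above 15 h, because the fast stops there by design.

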| Version 1.0 | 30 Jan 2019 | Original Protocol |
| Version 2.0 (Amendment 1) | 17 Feb 2020 | 
An overview of changes includes the following:
 
 • Assessments for vector shedding was added only for subjects that did not demonstrated clearance in Study 401GSDIA01 (Section 11.3.11, Table 1, and Table 2) • Section 6.2.3 was updated to reflect the number of ongoing studies with DTX401 as of December 2019 • A complete physical examination was added to the Week 260 (or end of study) and Early withdrawal visit (Table 1 and Figure 2) • The recommended target carbohydrate range of the prefasting challenge dinner meal was decreased from 20-30 g to 15-20 g, and the prefasting challenge cornstarch dose was decreased from 35 g to 5 g, to minimize a potential insulin spike that could result in abrupt hypoglycemia and to normalize baseline glucose levels (Section 11.4.1 and Table 1) • Blood sample collection for measurement of glucose and lactate levels was added at the beginning of the controlled fasting challenge to provide baseline levels (Sections 11.3.7.1 and 11.4.1, and Table 1) • Instructions for glucose and lactate samples collected during the fasting challenge were corrected to state that samples should be prepared and transported in accordance with the site's standard procedures (Sections 11.3.7.1 and 11.4.1, and Table 1) • Continuous glucose monitoring was added to collect supplemental information on glucose level trends throughout the study (Sections 11.4.2 and 13.5.3, and Table 1) • The exploratory study objective and endpoint related to morning glucose level were modified to glucose level due to the addition of continuous glucose monitoring (Sections 7, 13.5.4, and 13.1.3, and Figure 2) • Collection of blood for measurement of lipid levels was added on the morning of hospital admission for the fasting challenge (Section 11.4.1 and Table 1) • Collection of blood for measurement of cortisol, fatty acid, glucagon, insulin, and ketone levels was added at the beginning and end of the fasting challenge, or more frequently at the Investigator's discretion (Sections 11.3.7.2 and 11.4.1, and Table 1) • Details regarding the collection of morning glucose levels were clarified, including instances in which a subject is unable to use the assigned continuous glucose monitor (Section 11.4.2 and Table 1) • An enzyme-linked immunospot (ELISPOT) assay was added to assess any long-term potential cell-mediated immune responses to DTX401 (Sections 8.1, 11.3, 11.3.9.1, 13.6, Figure 2, and Table 1) • Text was added to clarify that the reporting period for hypoglycemic events is throughout the study (Sections 11.3.6 and 13.4.2) • The table of Clinical Laboratory Parameters was updated for completeness (Table 2) |

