| Version 3.0 (Amendment 2) | 23 Mar 2021 | 
Changes include the following:
 
 • The Sponsor’s address has been revised (Title Page). • The Coordinating Investigator for the study has been removed (Title Page and Section 13.2). • The Sponsor Contact was changed from PPD MD to PPD MD (Sponsor Signature). • The sample size was decreased from “approximately up to 18 subjects” to “approximately up to 12 subjects” based on current plans to end enrollment in Study 401GSDIA01 after Cohort 4 (Sections 2, 7.1.2, and 12.1.4). • The following changes were made to the controlled fasting challenge assessment (Table 1, Table 2, Sections 10.3.7.1, 10.3.7.2, 10.4.1, and 12.5.1): 
 ○ The definition of euglycemia for the end of the controlled fasting challenge changed from ≥ 60 mg/dL (≥ 3.33 mmol/L) to ≥ 54 mg/dL (≥ 3.0 mmol/L). ○ The composition of the dinner meal was updated from a prespecified carbohydrate range (15–20 g) to a personalized meal for each subject, including a target carbohydrate range and overall composition in protein, fats and dietary fiber that is as close as possible to the subject’s most current dinner prescription but not higher than the carbohydrate content of the dinner prescription recorded at their baseline visit in Study 401GSDIA01. ○ The prefasting cornstarch dose was updated from 5 g to match the respective subject’s most recent cornstarch prescription and timing post dinner, but not higher than the prescribed amount recorded at the baseline visit in Study 401GSDIA01. ○ Blood samples on the morning of the controlled fasting challenge were updated to include clinical chemistry (including lipid levels), hematology, coagulation panel, and urinalysis, to be sent to the central laboratory, and samples for AST and ALT levels to be sent to the local laboratory for STAT analysis. ○ Blood sample assessments at the beginning and end of the controlled fasting challenge were updated to include cortisol, ACTH, free fatty acids, glucagon, insulin, C-peptide, growth hormone, IGFBP1, alanine and ketone levels (3-hydroxy butyrate), and the instructions regarding laboratory sample collection before and during the controlled fasting challenge have been revised for clarity. ○ A final sample for glucose, lactate, growth hormone, IGFBP1, ACTH, and cortisol measurement has been added 30 minutes after the end of the controlled fasting challenge. |

| Version | Date | Summary of Changes |

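### SAP 6.8.1 summarises fasting-challenge duration by visit without flagging the pre-fast regimen or stopping threshold, both changed by amendment, and its per-gram ratios do not correct for load

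*SAP*

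**What the plan says.** **Test conditions.** The protocol's amendment history records two changes to what subjects receive before the fast.

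- Version 2.0 (17 Feb 2020): "the prefasting challenge cornstarch dose was decreased from 35 g to 5 g", and the carbohydrate target of the "prefasting challenge dinner meal was decreased from 20-30 g to 15-20 g".
- Version 3.0 (23 Mar 2021): "The prefasting cornstarch dose was updated from 5 g to match" the subject's own current prescription, with the Study 401GSDIA01 baseline prescription as a ceiling. The dinner moved "to a personalized meal for each subject, including a target carbohydrate range", under a similar ceiling. In the same amendment, "The definition of euglycemia for the end of the controlled fasting challenge changed from" 60 mg/dL or above to 54 mg/dL or above.

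Protocol 10.4.1 carries the Version 3.0 rules forward. It also provides for subjects who take no cornstarch before the fast.

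**Analysis.** SAP 6.8.1 brings in fasts from both studies and takes duration from the start and end times on the eCRF. On the main summary it says "Duration of CFC and change from baseline will be summarized by visit", with Day 0 of Study 401GSDIA01 as baseline. SAP 6.1 splits tables by cohort, Cohorts 2-4 combined, and overall. Section 6.8.1 names only the <54 mg/dL glucose rule and explains unequal loads by individual prescription alone.

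The same section plans by-visit summaries of pre-fast cornstarch and dinner carbohydrate, a listing, individual duration profiles and two ratios. The first is defined thus: "Normalized CFC duration will be calculated as CFC duration divided by the pre-CFC cornstarch (grams"). The second divides by dinner carbohydrate plus cornstarch. The SAP describes each as a gain in minutes per gram.

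**The concern.** The log differs from the current text because it records superseded rules, and that is not an error. The issue is that fasts run under superseded rules enter the same summaries as later ones. How long a fast lasts may depend on what was eaten beforehand, and it depends on the glucose level at which the fast is stopped. The protocol's stated reason for the Version 2.0 cut, to limit an insulin spike and to normalise starting glucose, treats the load as relevant to glucose during the fast.

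If fasts under different rules fall at different visits, or are mixed within a visit, part of any pattern over time could reflect the protocol version and not the subject. A reader of the SAP would not know this, because the amendments are not mentioned there. The per-gram ratios, offered because loads differ, could add a second artefact.

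**Working it through.** The plan states no figure to reproduce: the study is descriptive, with no power calculation.

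**1. Specified loads** (amendment history, Versions 2.0 and 3.0). Total = dinner carbohydrate + cornstarch.

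| Rules | Dinner | Cornstarch | Total | Glucose end level |
|---|---|---|---|---|
| Version 1.0 | 20-30 g | 35 g | 55-65 g | 60 mg/dL* |
| Version 2.0 | 15-20 g | 5 g | 20-25 g | 60 mg/dL |
| Version 3.0 onward | personalised, capped | own prescription, capped, may be 0 g | not given | 54 mg/dL |

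*The level replaced at Version 3.0; no earlier change is logged.

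Version 1.0 to 2.0: the fall is 55 − 25 = 30 g to 65 − 20 = 45 g, a factor of 55/25 = 2.2 to 65/20 = 3.25. Mid-range totals are 60 g and 22.5 g, a fall of 37.5 g. Cornstarch alone falls 35/5 = 7-fold.

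**2. Does the ratio remove load?** Ratio = minutes / grams. Take one 4 h (240 min) fast:

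- per gram of cornstarch: 240/35 = 6.9 and 240/5 = 48.0 min/g;
- per gram of total carbohydrate: 240/60 = 4.0 and 240/22.5 = 10.7 min/g;
- at 0 g of cornstarch: undefined.

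A ratio removes load only if duration is proportional to grams through zero. Suppose instead that duration = 120 min + 2 min/g × total grams (assumed values):

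- at 60 g: 240 min = 4.0 h, ratio 240/60 = 4.0 min/g;
- at 22.5 g: 165 min = 2.75 h, ratio 165/22.5 = 7.3 min/g.

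Raw duration falls while the ratio rises, with no change in the subject.

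**3. Illustrative shift in hours, Version 1.0 against 2.0.** If each gram adds 1, 2, 3 or 5 min (assumed), 37.5 g is worth 0.6, 1.3, 1.9 or 3.1 h. At 2 min/g the shift is 75 min. One such fast moves a 3-subject cohort mean by 75/3 = 25 min (0.42 h) and a 12-subject mean by 75/12 = 6.25 min (0.10 h).

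**4. Threshold.** Extra time = (60 − 54)/rate of glucose decline. At assumed rates of 5, 10, 20 and 30 mg/dL/h this is 72, 36, 18 and 12 min. It applies only to fasts ended by glucose, not to those ended by symptoms or at 15 h.

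**The case against.** The plan is not blind to load. By-visit summaries of cornstarch and dinner carbohydrate will sit beside duration, and the listing and individual profiles let a careful reader trace a fast. The total-carbohydrate ratio is less distorted than the cornstarch ratio: 10.7/4.0 = 2.7-fold against 7-fold in the example. Nothing is tested, so no error rate is at stake. All of this stands, and it limits the point to clarity of interpretation.

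A reader might go further and infer that mean duration will climb at later visits as 5 g fasts drop out, imitating a growing effect, while the normalised summary collapses. The documents do not support that, for four reasons.

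- **Comparator.** Fasts that follow the 5 g regimen use the subject's own prescription. That load is not given and may be zero. A shift built on 35 − 5 = 30 g compares Version 1.0 with 2.0, not 2.0 with 3.0.
- **Sign.** No minutes-per-gram slope is given. The insulin-spike rationale implies that a larger load could even shorten a fast.
- **Timing.** No dosing or fast dates are given. Study 401GSDIA01 was completed in November 2022 (Protocol 5.2.3) with 1 year of follow-up, so dosing could have run to about late 2021. Amendments normally take effect only after ethics and authority approval (Protocol 13.1.1), so document dates are not exact boundaries. Protocol 7.3 anticipates visits missed because of COVID-19, so 5 g fasts may be few.
- **Baseline.** The amendments belong to Study 401GSDIA02. Meal and stopping conditions at Day 0 are not in these documents.

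Restricting conclusions to load-matched fasts would also be wrong. Cornstarch use is itself a tertiary endpoint, so matching selects on a post-treatment outcome and drops the subjects who reduced cornstarch most.

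**Conclusion.** The point holds in limited form. It is documented that the specified pre-fast load changed twice and the glucose end level once, and that SAP 6.8.1 summarises fasts by visit with no regimen flag, giving individual prescription as the only reason for unequal loads. It follows from arithmetic alone that the per-gram ratios do not correct for load: for an identical fast they differ 7-fold (cornstarch) or 2.7-fold (total carbohydrate) between the Version 1.0 and 2.0 regimens, and the cornstarch ratio fails at 0 g.

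It is not established how many fasts fell under each set of rules, whether rules were mixed within a visit, or the size and direction of any bias in change from Day 0. The hour and minute shifts above rest on assumed slopes and decline rates and are illustrations only. With 3 subjects per cohort, a single fast under different rules can be visible in a cohort mean, which makes the change worth its small cost. No view is taken on which meal, dose or stopping rule is right.

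**What to change.** In SAP 6.8.1:

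1. **Flag the regimen.** For each fast in either study, derive the conditions actually applied: protocol version implemented at the site, recorded cornstarch and dinner grams, and stopping threshold. Show them in the CFC listing and on the individual duration plots, and state that conditions changed by amendment.
2. **Load-matched sensitivity summary.** Report raw duration and change from Day 0 for fasts whose total load lies within a fixed margin of that subject's Day 0 load (for example 10 g, to be set in advance). Give the number of fasts excluded and note that subjects who cut cornstarch most drop out. Do not make this the sole basis for statements over time.
3. **Common-threshold sensitivity summary.** Derive time to the first sample below 60 mg/dL from the serial samples, for analysis only. Define how fasts ended earlier by symptoms or at 15 h are shown. First confirm that the Study 401GSDIA01 fasts were run down to that level.
4. **Ratios.** Do not describe them as an adjustment for load or as a gain per gram. Set the cornstarch ratio to not calculable at 0 g and report how often this occurs.

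Cost: SAP wording and a few extra outputs. Protocol 10.4.1 already has grams, meal composition and times recorded; completeness for earlier fasts should be checked. The downside is small, selected numbers in the matched table.

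### The lactate rate of rise has no value when lactate never exceeds its starting level and can never be negative, and the SAP has no rule for either case

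*SAP*

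**What the plan says.** SAP 6.8.1 defines the rate of rise of lactate during the CFC as a slope in mmol/L/h, "calculated as the slope between the lactate value at the start of CFC and peak lactate value during the CFC". The peak is defined separately: "Peak analyte value during the CFC is the maximum analyte value observed any time from the start time of CFC" until it finishes. That set is stated as "including pre-CFC and end-CFC analyte values". The starting value is the sample nearest the start of the CFC, within 30 minutes either side. The rate "and change from baseline will be summarized by visit".

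The CFC has no fixed length. It ends on the first of three conditions: "1) glucose <54 mg/dL; 2) signs/symptoms of hypoglycemia; or 3) 15 hours fasting without hypoglycemia". Protocol 10.4.1 has lactate sampled about hourly, then about every 30 minutes once glucose is at or below 70 mg/dL.

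The glucose rate of decline in SAP 6.8.1 is built the same way, from start to trough, with the starting value in the trough set. Neither SAP 6.8.1 nor SAP Appendix 1 (missing data) says what to do when the starting value is itself the extreme.

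**The concern.** A rate meant to show how lactate behaves during fasting should take a value for every subject and be able to show a fall. This one does neither. The subjects for whom it has no value are those whose lactate never rose above its start, arguably the most favorable result. If that happens at one visit, the visit's value and its change from baseline are lost. If it happens at Day 0 of Study 401GSDIA01, every later change from baseline for that subject is lost. Tables are presented by cohort, and Study 401GSDIA01 enrolled cohorts of 3, so one undefined slope can remove a third of a row.

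The second worry is fast length. The length of the CFC is the secondary efficacy outcome and may differ between Day 0 and later visits. A maximum taken over more samples and more hours need not behave the same way at both.

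**Working it through.** The documents give no lactate values, variability or expected slope, so there is no planned figure to reproduce. Every lactate number below is an assumption; only the definitions and the sampling scheme come from the documents.

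**Algebra.** Write y0 for the lactate at start time t0, and yp for the peak at time tp. The SAP rate is

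rate = (yp - y0) / (tp - t0).

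Because y0 is in the peak set, yp ≥ y0 always, so the rate cannot be negative. If every later value is below y0, then yp = y0 and tp = t0, and the rate is 0/0. Both results follow from the text alone.

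**Effect on a mean (illustration).** Take 12 subjects, 6 with a steady rise of +0.3 mmol/L/h and 6 with a steady fall of -0.1, without noise.
- True mean: (6 × 0.3 + 6 × (-0.1)) / 12 = 1.2 / 12 = 0.10.
- SAP rate, undefined slopes dropped: (6 × 0.3) / 6 = 0.30.
- SAP rate, undefined slopes set to 0: (6 × 0.3) / 12 = 0.15.

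Both overstate the rise. Setting the slope to 0 keeps the subjects but still hides the falls.

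**Effect of noise.** Simulated straight-line profiles starting at 2.0 mmol/L, sampled hourly, with noise SD 0.3 mmol/L:

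| True slope (mmol/L/h) | Fast | Undefined | Mean of defined SAP rates |
|---|---|---|---|
| 0 | 4 h | 20% | +0.23 |
| 0 | 8 h | 11% | +0.17 |
| 0 | 12 h | not tabulated | +0.14 |
| 0 | 15 h | 6% | +0.12 |
| -0.1 | 8 h | about 40% | +0.22 |
| +0.3 | 8 h | not tabulated | +0.32 |

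For flat lactate the undefined share is 1 / (number of samples): 1/5, 1/9 and 1/16 at 4, 8 and 15 h. Going from a 4 h to a 12 h fast changes the mean by 0.14 - 0.23 = -0.09 with no true change. From 4 h to 15 h the spurious rate shrinks by 1 - 0.124/0.228 = 46%. The shrinkage is about 45% at SD 0.1 (0.076 to 0.042) and at SD 0.5 (0.376 to 0.209).

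A steady true rise also shrinks once noise is present, though less as it gets steeper: at +0.1, 0.24 at 4 h and 0.13 at 15 h; at +0.3, 0.36 and 0.31.

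**Effect of curve shape, no noise.** The denominator is time to peak, not fast length:

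| Curve | 4 h | 8 h | 15 h |
|---|---|---|---|
| Steady rise of 0.3/h | 0.30 | 0.30 | 0.30 |
| Peak of 4.0 at 1 h, then falling | 2.0 | 2.0 | 2.0 |
| Accelerating, 2·exp(0.1t) | 0.25 | 0.31 | 0.46 |
| Total rise of 3 spread over the fast | 0.75 | 0.375 | 0.20 |
| Flat, then 1.0/h in the last 2 h | 0.50 | 0.25 | 0.13 |
| Fall from 3.0 to 1.5 | 0/0 | 0/0 | 0/0 |
| Fall from 3.0 to 1.2, late rise to 2.8 | 0/0 | 0/0 | 0/0 |
| Fall from 3.0 to 1.2, late rise to 3.6 | 0.15 | 0.075 | 0.04 |

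So the rate can stay the same, grow or shrink as the fast lengthens. The last two rows show that the condition for 0/0 is that lactate never again exceeds its start, not that it falls at first.

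**The case against.** The best counter-argument is that little depends on this number. The SAP is descriptive throughout, with no hypothesis test and up to 12 subjects. The tertiary endpoint is lactate levels over time, not this rate. The SAP also summarizes pre-CFC lactate and CFC duration by visit, plots each subject's lactate curve and lists the values, so a falling profile would be seen. Protocol 5.1 describes lactate building up in prolonged hypoglycemia, and where lactate clearly rises the bias is small: at SD 0.3 a true slope of 0.5 gives 0.53 at 4 h and 0.51 at 12 h, and a slope of 1.0 gives 1.00 at both. The documents do not show that flat or falling profiles are common. All of this stands, and it limits the severity. It does not supply the missing rule or repair the mean and change-from-baseline table.

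A reader might infer that a longer fast makes the rate fall and so manufactures an improvement. The documents do not support that as a general result. Early peaks and noise-free steady rises are unaffected, accelerating curves look worse, and a given rise that truly takes longer is truly slower. The missing and never-negative cases work the other way, by hiding improvement. No net direction can be claimed.

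A reader might also infer that a least-squares slope should replace the planned rate. It recovers the truth when the profile is a straight line. For a flat course with a late 2 h rise it gives 0.50, 0.18 and 0.06 at 4, 8 and 15 h, which depends on length more than the SAP rate does (0.50, 0.25, 0.13). For an early peak that returns to its start it is negative (-0.13 at 4 h), which hides the excursion. The two measure different things, so adding one is easier to defend than substituting it.

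**Conclusion.** Two defects hold from the SAP text without any assumption: the rate is undefined when no later lactate exceeds the start, and it can never be negative. Followed literally, the by-visit mean and change from baseline omit subjects whose lactate stayed below its start, and noise turns flat or falling profiles into positive rates.

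The sizes rest on assumptions: noise SD 0.3 mmol/L (0.1 to 0.5 examined for flat lactate), a start of 2.0 mmol/L, straight-line truth, and hourly samples without the switch to 30 minutes. On those terms the spurious rate for flat lactate is +0.12 to +0.23 mmol/L/h over fasts of 15 to 4 h, and about 40% of profiles falling at 0.1 mmol/L/h over 8 h have no value. Dependence on fast length is possible, but its size and direction turn on the shape of the curve.

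Severity is minor, and the point is worth taking because the improvement is cheap.

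**What to change.** In SAP 6.8.1:

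1. Set the slope to 0 when the starting value is the peak, and report at each visit how many subjects this affects.
2. Keep the start-to-peak rate as planned.
3. Beside it, summarize a signed rate over the whole fast, with negative values allowed: either end-CFC minus pre-CFC lactate divided by hours, or a least-squares slope through all samples. Name the choice in advance. The first uses values the SAP already defines.
4. Summarize peak lactate by visit as a value of its own.
5. Apply the rule in step 1 to the glucose start-to-trough rate when the starting value is the trough. This should arise less often, since a fast that starts at or above 54 mg/dL and ends on glucose below 54 mg/dL has a trough below its start.

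The signed rate cures the sign problem and the gap. It does not remove dependence on fast length: for the late-rise curve, end minus start per hour is 2/4, 2/8 and 2/15, that is 0.50, 0.25 and 0.13, the same as the planned rate. It should therefore be read with CFC duration.

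The cost is a few lines of SAP text, one extra rate, one extra summary and a little programming on data already collected. Comparability with any peak-based rates from Study 401GSDIA01 is kept because the planned measure stays.
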